11.2 Definition of Baseline for Calculating Change

The Baseline Period is from Day 1 to Day 8. The baseline for calculating change from baseline will be defined in the following table.

Metric	Baseline	Corresponding post-baseline visits
Quit Attempts and Quitting Intentions	Day 1 (Visit 2)	Day 36 (Visit 7)
Fagerstrom Test for Cigarette Dependence (FTCD)	Day 8 (Visit 3)	Day 36 (Visit 7)
BOE	Day 8 (Visit 3)	Visits 4, 5, 6, 7
CPD daily tracking from IVRS	The average of available data from Day 2 through Day 8	Daily CPD Day 9 to 36 or the average of last week at Visits 4, 5, 6, 7
Vital Signs	Day 8, including unscheduled (rechecked) values	Visits 4, 5, 6, 7
*see Section 11.4.3 for more details		

Rationale for the baseline choices for calculating change:

Quit attempts and intentions: Day 1 is the only one measurement in baseline.

FTCD: There are 2 measurements in the baseline, Day 1 and 8. Day 8 is selected because it is anticipated that there will be changes in CPD, a key component of the FTCD score, when adult smokers are asked to track their daily cigarette consumption. Day 1 value does not reflect this change.

BOE: Day 8 is the last of the 2 baseline values and is closer to the post-baseline values.

CPD daily tracking: The weekly average was selected to adjust for the daily variability and also because total NNAL (primary end-point) has a longer half-life and the average CPD might be better representative of changes in exposure to total NNAL than the individual values.

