11.4.2 Statistical Analyses of Secondary Endpoints

Difference in baseline:

Paired T Test will be used to examine the difference in all 5 BOEs between Day 1 and Day 8.

Paired T test will also be used to examine the differences in CPD between the once weekly recall at Day 8 (from questionnaire) and the average daily tracking of CPD from Days 2 through 8 (from IVRS).

Difference in change from baseline:

Linear mixed model for repeated measures analyses of variance will be used for the analyses of the secondary outcome measures: percent change from baseline and absolute change from baseline in all other BOEs. The same model will be used for percent change from baseline and absolute change from baseline in CPD and Total score of FTCD, the model details are as follows:

For other BOEs:

Model 1:

Percent (or absolute) change from baseline = study group + visit+ study group*visit + subject + random error

Model 2:

Percent (or absolute) change from baseline = study group+ visit+ study group*visit + subject + CPD + sex + race + BMI + age + random error

For CPD and Total Score ofFTCD:

Model 1:

Percent (or absolute) change from baseline = study group+ visit+ study group*visit +subject+ random error

Model 2:

Percent (or absolute) change from baseline = study group+ visit+ study group*visit +subject+ sex + race + BMI + age + random error

where

CPD = fixed effect covariate representing average number of cigarettes per day for the past two days from IVRS

study group = fixed effect term (test or control)

sex = fixed effect (male or female)

age = fixed effect covariate (continuous)

race= fixed effect (White or Non-White)

BMI = fixed effect covariate (continuous)

visit= fixed effect term representing days (ordinal categorical variable)

subject = random effect

baseline = Day 8 value for BOE and average of Day 2 to 8 for CPD (IVRS)

If the study group*visit interaction term is not statistically significant (P-value > 0.10), then the interaction term will be removed from the model and all comparisons will be done using the overall product means. If the interaction effect is significant (P-value < 0.10), then the comparisons will be conducted for each study visit.

Least squared mean and standard error for the product effect will be estimated by study group and visit with p-values for statistical significance. P-value will also be provided for other effects in the model.

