APPENDIX 2: LIST OF TFLS FOR INTERIM AND FINAL ANALYSES

Following is the list of TFLs that will be produced during the interim analyses.

- Table 14.1-1 Summary of Subject Disposition
- Table 14.1-2 Summary of Screening Demographics
- Table 14.1-3 Summary of Baseline Smoking Characteristics
- Table 14.2.1-3.1 Individual Data and Summary Statistics of S-PMA
- Table 14.2.1-3.2 Individual Data and Summary Statistics of Change from Baseline S-PMA
- Table 14.2.1-3.3 Individual Data and Summary Statistics of Percent Change from Baseline S-PMA
- Table 14.2.1-4.1 Individual Data and Summary Statistics of Carboxyhemoglobin
- Table 14.2.1-4.2 Individual Data and Summary Statistics of Change from Baseline Carboxyhemoglobin
- Table 14.2.1-4.3 Individual Data and Summary Statistics of Percent Change from Baseline Carboxyhemoglobin
- Table 14.2.1-5.1 Individual Data and Summary Statistics of Exhaled Carbon Monoxide
- Table 14.2.1-5.2 Individual Data and Summary Statistics of Change from Baseline Exhaled Carbon Monoxide
- Table 14.2.1-5.3 Individual Data and Summary Statistics of Percent Change from Baseline Exhaled Carbon Monoxide
- Table 14.2.1-6.1 Individual Data and Summary Statistics of Cigarettes per Day
- Table 14.2.1-6.2 Individual Data and Summary Statistics of Change from Baseline Cigarettes per Day
- Table 14.2.1-6.3 Individual Data and Summary Statistics of Percent Change from Baseline Cigarettes per Day
- Table 14.2.1-7.1 Individual Data and Summary Statistics of Total Score of Fagerstrom Test for Cigarette Dependence
- Table 14.2.1-7.2 Individual Data and Summary Statistics of Change from Baseline Total Score of Fagerstrom Test for Cigarette Dependence
- Table 14.2.1-7.3 Individual Data and Summary Statistics of Percent Change from Baseline Total Score of Fagerstrom Test for Cigarette Dependence
- Table 14.2.1-X Individual Data and Summary Statistics of Urine Creatinine (Interim only)
- Table 14.2.1-8.1 Individual Data and Summary Statistics of VBM-FG2 Discs per Day

- Table 14.2.1-8.2 Individual Data and Summary Statistics of Change from Baseline VBM-FG2 Discs per Day
- Table 14.2.1-8.3 Individual Data and Summary Statistics of Percent Change from Baseline VBM-FG2 Discs per Day
- Listing 16.2.8-12 Other Tobacco or Nicotine Containing Product Use Questionnaire by Subject
- Table 14.2.1-12 Individual Data and Summary Statistics for Number of Quit Attempts with Change from Baseline

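### The FTCD model in SAP Section 11.4.2 carries visit, interaction and subject terms that a single post-baseline visit cannot support, and percent change suits a 0–10 score badly

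*SAP*

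**What the plan says.** Section 11.4.2 states: "The same model will be used for percent change from baseline and absolute change from baseline in CPD and Total score of FTCD". Model 1, given for the other biomarkers and repeated for CPD and FTCD, is "Percent (or absolute) change from baseline = study group + visit+ study group*visit + subject + random error". Model 2 for CPD and FTCD adds sex, race, BMI and age. The section then sets a rule for all these models: "If the study group*visit interaction term is not statistically significant (P-value > 0.10), then the interaction term will be removed from the model"; otherwise the groups are compared visit by visit.

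The table in Section 11.2 gives FTCD a Day 8 baseline and one later visit: "Fagerstrom Test for Cigarette Dependence (FTCD) Day 8 (Visit 3) Day 36 (Visit 7". The biomarkers, by contrast, have Visits 4 to 7. The rationale below the table adds "FTCD: There are 2 measurements in the baseline, Day 1 and 8", and selects Day 8 for calculating change.

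Section 11.1 forms percent change by dividing by the subject's own baseline and rules out imputation. Appendix 1 scores FTCD from 0 upward. The interim list in Appendix 2 includes "Table 14.2.1-7.3 Individual Data and Summary Statistics of Percent Change from Baseline Total Score of Fagerstrom Test for Cigarette Dependence" and "Table 14.2.1-8.3 Individual Data and Summary Statistics of Percent Change from Baseline VBM-FG2 Discs per Day".

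**The concern.** The model was written for endpoints measured at four post-baseline visits and then applied to one measured once. Comparing FTCD change between groups is a stated secondary objective (Section 5.3). As it stands, whoever programs it must decide which terms to drop and what to do with the interaction rule, and may do so after seeing the data.

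Percent change raises a second problem. The FTCD total is a short integer score that can be zero, so the ratio is undefined for some possible baselines and very sensitive at low ones. The table of percent change in discs per day has the same weakness if its baseline precedes dispensing.

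**Working it through.** The SAP states no sample size, power or precision figure for FTCD, so there is nothing to reproduce. The check concerns what the model can estimate.

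**Inputs.** 90 Test and 60 Control subjects (Section 6); model terms and interaction rule (Section 11.4.2); four post-baseline visits for biomarkers and one for FTCD (Section 11.2); percent-change formula and no imputation (Section 11.1); item scores (Appendix 1).

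**1. Degrees of freedom with all 150 subjects.**

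| | Biomarkers, 4 visits | FTCD, 1 visit |
|---|---|---|
| Records | 150 × 4 = 600 | 150 × 1 = 150 |
| Group | 1 | 1 |
| Visit | 4 − 1 = 3 | 1 − 1 = 0 |
| Group × visit | 1 × 3 = 3 | 1 × 0 = 0 |
| Rank of fixed effects, with intercept | 1 + 1 + 3 + 3 = 8 | 1 + 1 + 0 + 0 = 2 |
| Left after subject effects | 600 − 150 − 3 − 3 = 444 | 150 − 150 = 0 |

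For FTCD the interaction test does not exist, so the P > 0.10 rule cannot be applied.

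**2. Variance components.** With one record per subject, Var(y) = subject variance + residual variance, and the likelihood depends only on that sum. In a simulated example with a total of 2.25, the splits 0 + 2.25, 0.5 + 1.75, 1 + 1.25, 1.5 + 0.75 and 2.0 + 0.25 all give the same log-likelihood, −256.39.

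**3. What survives.** The group contrast is estimable in the one-visit design. It is the two-group comparison at Day 36, with 150 − 2 = 148 residual degrees of freedom. The Day 1 score does not help, because it adds no post-baseline record.

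**4. Percent change.** The formula is 100 × (Day 36 − Day 8) / Day 8. The Appendix 1 items give 4 × 2 × 2 × 4 × 2 × 2 = 256 response patterns with totals from 0 to 10, and exactly one pattern totals 0. A 1-point change is:

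| Day 8 score | 0 | 1 | 2 | 5 | 10 |
|---|---|---|---|---|---|
| Percent change | undefined | 100% | 50% | 20% | 10% |

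The share of subjects scoring 0 is not in the SAP. Assuming 1%, 2%, 5% or 10% of 150, the expected number without a percent change is 1.5, 3, 7.5 or 15.

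**5. Illustrative power, on assumed inputs only.** Rounded scores limited to 0–10 were simulated with mean 3.5 to 5.0, SD 2.2, measurement SD 0.9, a true difference of 0.6 points, 90 against 60 subjects and 3,000 trials per setting. The last column adds between-subject variation in change (SD 1.0).

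| Analysis | Base setting | With added variation |
|---|---|---|
| Percent change | about 0.60 | about 0.42 |
| Absolute change | 0.73–0.76 | 0.53–0.56 |
| ANCOVA | 0.76–0.79 | 0.56–0.57 |

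With the lowest baseline set to 1, so that nobody is lost, percent change reached 0.58–0.59. The ordering is stable; the levels depend on the assumptions.

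**6. Disc tables.** Section 11.2 defines no baseline for discs per day, and Section 6 starts ad libitum use only after the Day 8 IVRS call. A pre-dispensing baseline would be 0. Percent change is then undefined, while absolute change equals the post-baseline value.

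**The case against.** The strongest reply is that the FTCD objective is not endangered. Sections 5.3 and 11.3.2 ask for change in FTCD, not percent change. Section 11.4.2 plans absolute change as well, which is defined at a baseline of 0 and loses nobody. It also compares the groups on increase, no change or decrease in FTCD by a Mantel-Haenszel chi-square test, which needs neither a visit term nor division by baseline. An analyst who removes the empty terms reaches the Day 36 comparison at once. All of this stands and limits the harm. It does not make the written model or its interaction rule executable.

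A reader might infer that subjects will drop out of the FTCD analysis. The SAP does not show that. Loss affects the percent-change version only, and only if someone scores 0 on Day 8. The SAP gives no CPD eligibility limit; a protocol minimum above 10 cigarettes per day, if it still held on Day 8, would make the lowest score 1.

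A reader might also infer that both disc change tables are impossible. Table 14.2.1-8.2 (absolute change) can be computed and would merely repeat Table 14.2.1-8.1. The separate TFL shells, not available here, may define a disc baseline, and Section 14.2 allows a blank display where data are insufficient.

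**Conclusion.** The point holds in limited form. Sections 11.2 and 11.4.2 do not fit together for FTCD: visit and interaction have 0 degrees of freedom, the subject variance is not identifiable, and the interaction rule has nothing to act on. This follows from the SAP text without any assumption. An FTCD score taken at early termination would not rescue the model, since each subject would still have one post-baseline record and the secondary analyses use per-protocol completers only.

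It would be tempting to call the whole FTCD analysis not estimable. That is wrong: the Test–Control difference at Day 36 is estimable.

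The percent-change version is badly scaled for any low baseline and undefined at 0. How many subjects that affects is unknown. The power figures only illustrate the direction of the loss, because the SAP gives no FTCD distribution or effect and makes no FTCD power claim. For one secondary endpoint in a pilot this is modest, but it should be corrected before database lock.

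**What to change.** In Section 11.4.2, separate FTCD from CPD and give it its own model:

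- **Model 1:** Day 36 FTCD score (or absolute change from Day 8) = study group + Day 8 score + random error.
- **Model 2:** the same, plus sex, race, BMI and age.
- No visit, interaction or random subject term, and no interaction rule.

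With the Day 8 score as covariate, the score and the absolute change give the same group estimate. At 150 subjects, Model 1 leaves 150 − 3 = 147 residual degrees of freedom and Model 2 leaves 150 − 7 = 143. Day 8 scores are already collected. The gain of ANCOVA over plain absolute change is small (0.01 to 0.04 in the illustration); the main benefit is a model that can be run as written.

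Delete the FTCD percent-change analysis and Table 14.2.1-7.3. Remove Table 14.2.1-8.3 for discs; Table 14.2.1-8.2 may stay but would be redundant with a zero baseline. Make the same changes in the TFL shells.

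The cost is a few lines of SAP text and fewer tables. The downside is that no percent figure will be reported for FTCD.

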11.3.2 Secondary Endpoints

The secondary outcome measures or endpoints are:

- Differences in all BOE during the Baseline Period between Day 1 (weekly recall) versus Day 8 (daily tracking using IVRS).
- Difference in CPD during the Baseline Period between once weekly recall (Days 1 and 8) versus daily tracking (average of recordings on Days 2 through 8).
- Differences in the percent change from Baseline to EOS in BOE (urinary NE, S-PMA, blood COHb, exhaled CO) and CPD between the Test and Control Groups.
- Differences from Baseline to EOS in all BOE and CPD between the Test and Control Groups.
- Proporation of subjects in subgroups based on cigarette consumption change from Baseline to EOS (no change, <50% reduction, 50% reduction, 100% reduction, increase) within and between the Test and Control Groups.
- Proporation of subjects in subgroups based on total NNAL change from Baseline to EOS (no change, reduction, increase) within each group.
- Changes from Baseline (Day 8) to EOS in total scores of Fagerstrom Test for Cigarette Dependence (see Appendix 1), within and between the Test and Control Groups.
- Changes from Baseline (Day 1) to EOS on the Quit Attempts and Quitting Intentions, within and between the Test and Control Groups.

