All secondary and exploratory analyses will be conducted on the Per-protocol population only.

A linear regression analysis will be conducted within each group at each timepoint to examine the relationships between levels of all 5 BOEs (dependent variable) with either weekly cigarette counts (Day 1 and 8 from questionnaire) or daily cigarette counts (from IVRS) (independent variable). For total NNAL, the corresponding daily cigarette counts from IVRS will be the average of past 7 days. For other biomarkers, it will be the average of past 2 days. The regression analysis will be conducted on the Per-protocol population.

The proportion of subjects in subgroups will be provided with proportion and sample size based on:

- 1) Cigarette consumption change from Baseline (average of Days 2 to 8 from IVRS) to the last week (no change, <50% reduction, 2::50% reduction , 100% reduction, increase);
- 2) Total NNAL change from Day 8 to the last visit (no change, reduction, increase);
- 3) Total scores of FTCD change from Day 8 to the last visit (increase, no change, decrease)
- 4) Proportion of subjects in subgroups based on Changes from Baseline (Day 1) to EOS (increase, no change, decrease) on the change in Quit Attempts from Day 1 to last visit.
- 5) Proportion of subjects in subgroups based on Changes from Baseline (Day 1) to EOS (yes to no, no to yes, and same) on the change in Quitting Intentions from Day 1 to last visit.

The Mantel-Haenszel Chi-Square Test will be used for (1), (2), (3), and (4); Fisher exact test will be used for (5) to test the frequency differences between the two groups.

Additional statistical analyses:

Wilcoxon signed rank test will be used to test the FTCD score difference between the 2 baseline measures (Visit 2 and 3) for the test group. If there is no statistical significance, the average score will be related to the average amount of VBM-FG2 in the past week via linear regression. Otherwise the FTCD score for Visit 3 will be used.

For the test group only, a simple linear regression model will be used to examine the relationship between COHb and Exhaled CO at each post-baseline visit.

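### The FTCD total score has one post-baseline visit, yet SAP 11.4.2 assigns it the repeated-measures model and the interaction rule, several terms of which cannot be estimated for it

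*SAP*

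**What the plan says.** The comparison of FTCD change within and between groups is a secondary objective (SAP 5.3) and a secondary endpoint (SAP 11.3.2): "Changes from Baseline (Day 8) to EOS in total scores of Fagerstrom Test for Cigarette Dependence".

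The baseline table in SAP 11.2 has the row "Fagerstrom Test for Cigarette Dependence (FTCD) Day 8 (Visit 3) Day 36 (Visit 7"). In the same table the biomarkers have Visits 4, 5, 6 and 7 after baseline, and CPD has daily values or weekly averages at those four visits. The rationale below the table says of FTCD: "There are 2 measurements in the baseline, Day 1 and 8". It chooses Day 8, so the Day 1 score is not a response either.

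SAP 11.4.2 then says: "The same model will be used for percent change from baseline and absolute change from baseline in CPD and Total score of FTCD". The equations under the joint heading for CPD and FTCD contain study group, visit, their interaction, subject and random error. Model 2 adds sex, race, BMI and age. Visit is defined as a categorical fixed effect and subject as a random effect. The interaction is to be dropped if its P-value exceeds 0.10. Otherwise, "If the interaction effect is significant (P-value < 0.10), then the comparisons will be conducted for each study visit". Least squares means are requested by group and visit. No exception is made for FTCD.

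Later in 11.4.2 a separate categorical analysis of "Total scores of FTCD change from Day 8 to the last visit" (increase, no change, decrease) is planned with a Mantel-Haenszel chi-square test. All secondary analyses use the per-protocol population, which SAP 10 limits to subjects who completed the study without major violations.

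**The concern.** The model was written for outcomes measured at several visits. The block for CPD and FTCD leaves out the CPD covariate but keeps every repeated-measures term, although FTCD supplies only one change score per subject. A programmer following the text would ask for tests that do not exist for this endpoint, and would then have to decide alone which terms to remove and which denominator degrees of freedom to use. The SAP introduction requires substantial deviations to be agreed and identified in the study report, so this is better settled in the text before the analysis than improvised during it.

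**Working it through.** The SAP gives no figure on this point, so there is none to reproduce. The check counts degrees of freedom for Model 1.

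**Inputs**
- 90 Test and 60 Control subjects (SAP 6). The per-protocol set will be smaller, but the zeros below do not depend on N.
- Four post-baseline visits for the biomarkers and weekly CPD, and one for FTCD (SAP 11.2).
- Model terms as listed in SAP 11.4.2.

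**Step 1: sequential ranks.** Let X hold the intercept, group, visit and group-by-visit columns, and Z the subject indicators. The degrees of freedom of each term are the increase in rank when it is added. Residual degrees of freedom are the number of records minus rank[X Z].

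| Term | Four visits | One visit (FTCD) |
|---|---|---|
| Records | 600 | 150 |
| Group | 1 | 1 |
| Visit | 3 | 0 |
| Group-by-visit | 3 | 0 |
| Subject (within group) | 148 | 148 |
| Residual | 600 - 156 = 444 | 150 - 150 = 0 |

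Here 156 = 1 + 1 + 3 + 3 + 148 and 150 = 1 + 1 + 0 + 0 + 148. With one visit, the visit column equals the intercept and the interaction column equals the group column, so X has rank 2 with four columns.

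**Step 2: variance components.** With one record per subject, the variance of a change score is the subject variance plus the residual variance, and only that sum enters the likelihood. Numerically, ZZ' and the identity matrix are the same matrix with one visit (rank 1) and linearly independent with four (rank 2). On simulated single-visit data with the total variance held at 2, the REML log-likelihood was -120.5385 for subject variances of 0, 0.5, 1.0, 1.5 and 1.9 alike.

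**Step 3: the decision rule.** A term with 0 degrees of freedom has no P-value, so neither the P > 0.10 nor the P < 0.10 branch can be triggered.

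**Step 4: what survives.** Removing the redundant terms leaves change = group + error, with 1 degree of freedom for group and 150 - 2 = 148 for error. In one simulated fit that kept the random subject effect, the software split the variance as 0.854 and 0.854. The sum is 1.708, and sqrt(1.708 × (1/90 + 1/60)) = 0.218. The ordinary standard error of the change-score difference in that simulation was 0.219. The arbitrary split therefore leaves the standard error of the group difference essentially unchanged.

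**Step 5: baseline adjustment.** Assume equal variances s² at Day 8 and Day 36 and correlation r. The change score has variance 2s²(1 - r), and the ANCOVA residual has s²(1 - r²). The standard-error ratio is sqrt((1 + r)/2):
- r = 0.69: sqrt(0.845) = 0.919, about 8% smaller.
- r = 0.81: sqrt(0.905) = 0.951, about 5% smaller.

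Both correlations are assumed; the SAP gives none.

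**Step 6: percent change.** SAP 11.1 divides by the subject's baseline value. Every item in Appendix 1 can score 0, so the total can be 0 and percent change is then undefined.

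**The case against.** The strongest reply is that this is a template carried over, with little consequence. The Day 36 difference and its standard error are those of a two-sample comparison of change scores, as Step 4 shows. With one visit, the overall product mean is the Day 36 mean, so both branches of the rule would lead to the same contrast and no data-driven choice arises. The zero denominator degrees of freedom depend on the method used, and the SAP fixes none. The categorical Mantel-Haenszel analysis gives a working between-group test of FTCD change whatever happens to the model. No change-from-baseline model in the SAP includes the baseline value, so its absence is not peculiar to FTCD.

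All of this stands, and it limits the point. A reader might infer that the FTCD comparison cannot be obtained, or that the result would be biased. The documents do not support either: only the redundant terms are lost. A reader might also take the 8% or 5% as the size of the error. It is not; it rests on assumed correlations and describes a benefit of the replacement.

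What the reply does not remove is the error in the text. Nothing elsewhere in the SAP exempts FTCD or adds a visit. The Day 1 score is a baseline measurement. An early-termination assessment would still give one record per subject, and non-completers are outside the per-protocol set. The Mantel-Haenszel test compares direction of change and does not estimate a mean difference.

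**Conclusion.** The point holds in a limited form. For FTCD, Section 11.4.2 specifies a model and a decision rule that cannot be carried out as written: visit and group-by-visit have 0 degrees of freedom, the subject variance is confounded with the residual, and the interaction rule has no P-value. Depending on the degrees-of-freedom method, the group test may also lack a denominator. These results are structural and rest on no assumed effect, variance or correlation.

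The size is modest. One secondary endpoint of a pilot study is affected, and its group difference and total variance remain estimable. The primary analysis and the models for the other biomarkers and CPD are sound in this respect. The text should be corrected, but no conclusion of the trial depends on it.

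**What to change.** In SAP 11.4.2:
- Remove FTCD from the repeated-measures model, the interaction rule and the request for means by visit. Keep these for CPD and the biomarkers.
- Analyse absolute FTCD change from Day 8 to Day 36 by a single-time-point ANCOVA. Model 1: study group and Day 8 FTCD. Model 2: the same plus sex, race, BMI and age.
- Report the Test-Control difference and the within-group mean changes, each with a 95% confidence interval.
- State what happens to the planned percent-change analysis of FTCD: either drop it with a reason, or keep it with a stated rule for a Day 8 score of 0. Bring the percent-change table for FTCD in Appendix 2 into line.

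Dropping visit, group-by-visit, random subject and the rule is the minimum correction. Adding the Day 8 score uses data already collected and costs one degree of freedom (147 error degrees of freedom in Model 1 at N = 150, fewer in the per-protocol set). The cost is a few lines of SAP text and a simpler SAS call. No new data are needed.
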